Section 1.3 – Schedule of Events, (Table 1, Schedule of Events [Dose Escalation] and Table 2, Schedule of Events [Dose Expansion – Relapsed/Refractory Acute Myeloid Leukemia])	Revised “Bone marrow aspiration and/or biopsy” to “Blood and/or bone marrow aspiration and/or biopsy.” Revised footnote o (Table 1) and footnote n (Table 2) to “Whole blood and/or bone marrow samples will be collected and provided to a central laboratory for CCI [REDACTED] analyses.” Added footnote y to state that, “Bone marrow aspiration or biopsy will include local immunophenotyping, cytogenetic analysis, and molecular genetic testing. Additional procedural details are available in Section 6.1.10.3, Section 6.1.10.13, and Appendix 17.” Footnote y symbol was added to “Tumor evaluation/imaging.”	Revisions made to clarify biological sample collection and testing requirements.

Section Number	Summary of Change	Rationale for Change
Section 1.3 – Schedule of Events, Table 2 – Schedule of Events (Dose Expansion – Relapsed/Refractory Acute Myeloid Leukemia)	
Revised table title to add, “Relapsed/Refractory Acute Myeloid Leukemia.”
 
Added “Minimal residual disease evaluation” with timing to match “Tumor evaluation/imaging.”
 
Removed “Ann-Arbor staging” and associated footnote v. Subsequent footnote was relettered v.
	
Table title revision was made for clarity.
 
Evaluation was added to allow for proof-of-concept evaluation of relevance of minimal residual disease.
 
Ann-Arbor staging removed because of the removal of AITL cohort.

Section 2.1.2.2 – Mutations and Malignancies, Section 2.3.1 – Benefit-Risk Assessment	Added a statement that patients who fail IDH inhibitor therapies do not have any standard treatment options available.	Revision provides justification for modification of patient population for Part 2.
Section 2.2 – Background	Added language consistent with the “Study status as of Protocol Amendment 5” section of the synopsis and the Amendment Summary	Language was added to explain the study status and reason for the amendment.

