- ^u Survival follow-up should be performed every 12 weeks (\pm 2 weeks) after the EOT Visit. Additional details are provided in Section [6.1.19](#).
- ^v If tumor evaluation shows progressive disease during previous cycle and new drug has been dispensed, patient must return all unused study drug on 30-day safety visit after EOT.
- ^w Applicable for patients with AITL; see [Appendix 13](#) for a description of Ann-Arbor staging.

Amendment 5

- x Additional procedural details for risk stratification/prognostic stratification and scoring are available in Section [6.1.14.1](#).
- y Bone marrow aspiration or biopsy will include local immunophenotyping, cytogenetic analysis, and molecular genetic testing. Additional procedural details are available in Section [6.1.10.3](#), Section [6.1.10.13](#), and [Appendix 17](#).

Table 2 Schedule of Events (Dose Expansion - Relapsed/Refractory Acute Myeloid Leukemia)

Cycle/Period	Pre-screening	Screening	C1				C2		C3+	EOT	Safety Follow-up	Efficacy Follow-up	Survival Follow-up
			D1	D8	D15	D22	D1	D15	D1	Within 7 days after last dose	30 days after EOT Visit	Every 12 weeks from EOT Visit	Every 12 weeks from EOT Visit
Visit													
Visit window (days)			-28 to -1	-7 to -1	0	±1	±1	±1	±1	±3	±3	±7	±14
Activities													
Pre-screening informed consent	X												
Main informed consent ^a		X											
mIDH status ^b		X											
Medical history and demographics ^c	X	X											
Prior and concomitant medications and concomitant procedures ^d		X		X	X	X	X	X	X	X	X	X	
Height ^e		X											
Physical examination, vital signs, and weight ^e		X		X	X	X	X	X	X	X	X	X	
ECOG performance status ^e		X		X		X		X	X	X	X	X	
Ophthalmologic examination ^f		X							X (±1 week)		Every 12 weeks from C4D1 (±7 days)		
Laboratory evaluations: ^e													
Hematology ^g			X		X	X	X	X	X	X	X	X	
Blood chemistry ^h			X		X	X	X	X	X	X	X	X	
Blood amylase and lipase			X		X	X	X	X	X	X	X	X	

Cycle/Period	Pre-screening	Screening	C1				C2		C3+	EOT	Safety Follow-up	Efficacy Follow-up	Survival Follow-up
			D1	D8	D15	D22	D1	D15	D1	Within 7 days after last dose	30 days after EOT Visit	Every 12 weeks from EOT Visit	Every 12 weeks from EOT Visit
Visit													
Visit window (days)		-28 to -1	-7 to -1	0	±1	±1	±1	±1	±1	±3	±3	±7	±14
Activities													
Fasting lipid panel ⁱ			X						X		X	X	
Coagulation indicators ^j			X				X	X	X			X	
HbA1C			X				X			X	X	X	
Pregnancy test ^k		X	X	X			X			X	X	X	
Urinalysis ^l			X				X			X			

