Virological screening ^m		X											
Bone marrow aspiration and/or biopsy ⁿ													
PK and PD assessments													
12-lead ECG ^o													
ECHO/MUGA scan ^p		X		X					X		Cycle 3 Day 1 and every odd cycle thereafter	X	
Tumor evaluation/imaging		X		Every 8 weeks (±7 days) during the first 24 weeks and every 12 weeks (±14 days) thereafter						X		X	
Minimal residual disease evaluation		X		Every 8 weeks (±7 days) during the first 24 weeks and every 12 weeks (±14 days) thereafter						X		X	
Blood transfusion history ^q		X										X	
Blood transfusion record ^r			X	X	X		X	X	X	X	X		
Drug/dispense/return ^u				X				X		X			

Cycle/Period	Pre-screening	Screening	C1				C2		C3+	EOT	Safety Follow-up	Efficacy Follow-up	Survival Follow-up
			D1	D8	D15	D22	D1	D15	D1	Within 7 days after last dose	30 days after EOT Visit	Every 12 weeks from EOT Visit	Every 12 weeks from EOT Visit
Visit													
Visit window (days)			-28 to -1	-7 to -1	0	±1	±1	±1	±1	±3	±3	±7	±14
Activities													
Study drug administration													
AEs ^s	X	X	X	X	X	X	X	X	X	X	X	X	
Survival Follow-up ^t													X
-													
Risk stratification/Prognostic scoring ^v		X											

AE=adverse event; aPTT=activated partial thromboplastin time; C=cycle; D=day; ECG=electrocardiogram; ECHO=echocardiogram; ECOG=Eastern Cooperative Oncology Group; EOT=end of treatment; HbA1C=hemoglobin A1C; ICF=informed consent form; IDH=isocitrate dehydrogenase; INR=international normalized ratio; mIDH=mutant IDH; MUGA=multigated acquisition; OCT=optical coherence tomography; PD=pharmacodynamics; PK=pharmacokinetics; PR=partial response; PT=prothrombin time.

- a Procedural details are available in Section [5.1.1](#).
- b Patients should have a local report of IDH mutational analysis, confirming mIDH.
- c Procedural details for medical history and demographics are available in Section [6.1.3](#).
- d Procedural details for prior and concomitant medications/treatments are available in Section [6.1.4](#).
- e Procedural details are available in Section [6.1.6](#) (vital signs), Section [6.1.7](#) (physical examination, weight, and height), Section [6.1.8](#) (ECOG performance status), and Section [6.1.10](#) (laboratory evaluations).

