6.1.10.3 Hematology – Bone Marrow Aspiration and/or Biopsy

It is necessary to perform either bone marrow aspiration or biopsy, both are not mandatory. Patients with AITL that have fluorodeoxyglucose (FDG)-avid disease and will undergo positron emission tomography-computed tomography (PET-CT) imaging for screening and efficacy evaluation are not required to have a bone marrow aspiration or biopsy.

Bone marrow aspiration and/or biopsy examinations will be performed during screening, on Day 1 of Cycles 3, 5, and 7 (every 8 weeks \pm 7 days, for the first 24 weeks), then every 3 cycles (\pm 14 days) thereafter (ie, Day 1 of Cycles 10, 13, and so on), at the EOT visit, and at every efficacy follow-up assessment for applicable patients. Additional bone marrow examinations may be performed at the investigator's discretion on as-needed basis.

Results of the analyses of the morphology examination, immunophenotyping, cytogenetics, and molecular genetic testing performed during screening will be collected in the electronic case report form (eCRF).

Please refer to [Appendix 17](#) for a description of the immunophenotyping, cytogenetics, and molecular genetic testing for AML, HR-MDS, and AITL.

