APPENDIX 8 2017 EUROPEAN LEUKEMIANET EFFICACY CRITERIA FOR AML

Treatment Response	Efficacy Criteria
Complete response (CR)	
 • Myeloblast percentage <5% • Blast cells without Auer bodies • No blast cells in peripheral blood • No extramedullary lesion • ANC $\geq 1.0 \times 10^9/L$, PLT $\geq 100 \times 10^9/L$
Complete response with negative minimal residual disease (CR _{MRD})	
 • CR with negative RT-qPCR or CR with negative MFC
Complete response with incomplete count recovery (CRI)	
 • Meets all other criteria of CR but ANC $< 1.0 \times 10^9/L$ or PLT $< 100 \times 10^9/L$
Morphologically leukemia-free status (MLFS) ^a	
 • Myeloblast percentage <5% • Blast cells without Auer bodies • No extramedullary lesion • No hematological recovery requirements
Partial response (PR)	
 • Meets all hematological criteria for CR • The percentage of myeloblasts decreases from baseline by least 50% and reaches 5% to 25%
Stable disease (SD) ^b	
 • Fails to meet criteria for CR, CRI, CR_{MRD}, MLFS, PR, or progressive disease
Progressive disease ^{c, d}	
 • Increase in bone marrow blast percentage and/or absolute peripheral blood blast cells 
 – The percentage of myeloblasts increases from baseline by >50% (if blast cells at baseline are <30%, net increased value needs to be $\geq 15\%$); or percentage of myeloblasts >70% continues for at least 3 months; ANC is not seen to be improved by at least 100%, reaching ($>0.5 \times 10^9/L$ and/or PLT reaches $>50 \times 10^9/L$, without blood transfusion); or – The absolute peripheral blood blast cell count (WBC \times blast cell ratio) increases by >50% and reaches $>25 \times 10^9/L$ (without differentiation syndrome); or • New extramedullary diseases • After achieving CR/CR_{MRD}/CRI, $\geq 5\%$ of the blast cells recur in the bone marrow; or • Blast cells occur in the peripheral blood; or • Extramedullary lesions occur
Hematologic recurrence	

AML=acute myeloid leukemia; ANC=absolute neutrophil count; CR=complete response; MFC=multiparameter flow cytometry; PLT=platelet; RT-qPCR=quantitative reverse transcription polymerase chain reaction; WBC=white blood cell.

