4.2. Efficacy Endpoints

4.2.1. Best Overall Response

Assessment of anti-tumor response for patients with AML will be conducted according to 2017 European Leukemia Net (ELN) criteria (Döhner et al, 2017). Best overall response (BOR) is defined as the best response during the anti-tumor evaluation period, which will be determined using time point responses (TPRs) from date of the first dose of study treatment from Cycle 1 in continuous cycle (i.e. not from the date of single oral dose from the PK week for the dose escalation part) up until the last evaluable TPR prior to or on the date of (i) disease progression (at least 2 cycles of study drug should be administered to determine PD) / relapse according to the 2017 ELN criteria, or death; or (ii) withdrawal of consent or lost to follow-up; or (iii) receiving subsequent anti-cancer therapy, whichever is earlier.

The hierarchical order of these response categories is complete response with negative minimal residual disease (CR_{MRD-}) > complete response (CR) > complete response with partial hematological recovery (CRh) > complete response with incomplete count (CRI) > morphologically leukemia-free state (MLFS) > partial response (PR) > stable disease (SD) > progressive disease (PD) > NE (not evaluable), where CR_{MRD-} , CR and CRI are based on investigator assessment of response, and CRh will be derived from relevant data including investigator-collected bone marrow and hematology data by medical team as external file, as CRh is not defined in ELN 2017. This order will be used to derive the BOR. For example, a patient who has 4 anti-tumor assessments during the anti-tumor evaluation period with response being MLFS, PR, SD, and PD respectively, then the BOR for this patient will be MLFS.

Of note, for the BOR being SD, it is expected that the duration of SD lasts for at least 3 cycles, for example, if a patient only has one tumor assessment at 2 cycles with response being SD, then, the BOR for this patient will be NE instead. For the BOR being PD, at least 2 cycles of study drug should be administered, for example, if a patient only has one tumor assessment at 1 cycle of study drug with response being PD, then, the BOR for this patient will be NE instead.

Moreover, subjects who do not have post-dose tumor assessment, but have clinical progression as noted by the investigator or have died due to any cause before their second post-dose tumor assessment, BOR will be PD.

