5. ANALYSIS METHODS

5.1. General Principles

5.1.1. General Methodology

In general, all efficacy, safety and PK variables will be summarized using descriptive statistics and graphs as appropriate. Continuous variables will be summarized by descriptive statistics (observed number (n), mean, standard deviation, minimum, 25% percentile (Q1), median, 75% percentile (Q3), and maximum). Categorical variables will be summarized in frequency tables (frequencies and percentages).

Time to event variable will be analyzed using Kaplan-Meier method and summarized with median, 25% and 75% percentiles with their corresponding 95% confidence intervals (CI) which are calculated from a log-log transformation based on the method by [Brookmeyer and Crowley \(1982\)](#). Individual data will be presented in patient listings.

Analyses will be implemented using SAS Enterprise® Version 8.3 or higher (SAS Institute, Cary, North Carolina, USA). The International Conference on Harmonization (ICH) numbering convention, i.e. ICH-E3, will be used for all tables and listings.

Unless otherwise specified, analyses will be summarized:

- Efficacy analysis: by dose level for escalation stage (part 1) and by disease type for dose expansion (part 2).
- Analysis besides efficacy: by dose level and total for escalation stage (part 1) and by disease type and total for dose expansion (part 2).

In addition, main efficacy analysis will be repeated by IDH naïve/treated status (as defined in [Section 5.2.4](#)) and dose level for escalation stage (part 1) and by disease type for dose expansion (part 2).

Analysis will be conducted on the basis of first dose of study drug that a patient received. Hence, all summary tables, listings, and figures (TLFs) will be presented by treatment groups as defined in [Table 13](#).

Table 13 Group Display in TLFs

Part of the study	Treatment Group	Treatment Description in Data Display
Part 1 - Dose Escalation	1	Cohort 1- XX mg
	2	Cohort 2- XX mg
	3	Cohort 3- XX mg
	4	Cohort 4- XX mg
	5	Cohort 5- XX mg
	6	Cohort 6- XX mg
	7	Cohort 7- XX mg
	8	Cohort 8- XX mg
Part 2 - Dose Expansion at HMPL-306 XX mg*	1	Cohort A: AML

*As only one patient at HMPL-306 [REDACTED] mg was enrolled in Part 2 Dose expansion Cohort A, this patient will be combined into Part 1 Dose escalation Cohort 8 [REDACTED] mg in all the summary tables and figures.

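### CR_MRD- is reported as a percentage of all efficacy patients, but MRD testing is scheduled only in Part 2 (one patient), so the figure is a lower bound

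*SAP*

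**What the plan says.** **Ranking and source.** SAP 4.2.1 opens the ranking with CR_MRD-: "The hierarchical order of these response categories is complete response with negative minimal residual disease", with CR next below. It states that CR_MRD-, CR and CRi "are based on investigator assessment of response".

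**Test needed.** Protocol Appendix 8 defines CR_MRD- as "CR with negative RT-qPCR or CR with negative MFC".

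**Schedule.** Protocol Table 2 (dose expansion) has a row "Minimal residual disease evaluation" at screening and at each tumor evaluation. Protocol Table 1 (dose escalation) has no such row. Its footnote y, attached to the tumor evaluation row, says: "Bone marrow aspiration or biopsy will include local immunophenotyping, cytogenetic analysis, and molecular genetic testing". On recording that work-up, Protocol 6.1.10.3 mentions screening only: the results of "molecular genetic testing performed during screening will be collected in the electronic case report form (eCRF").

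**Who was enrolled.** The footnote to SAP Table 13 says that one patient only "was enrolled in Part 2 Dose expansion Cohort A, this patient will be combined into Part 1", in Cohort 8.

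**Reporting.** SAP 5.2.9.1 gives n and % for each best overall response category. The denominator is the efficacy analysis set (SAP 3.1.4 and 5.2.9), meaning everyone dosed from C1D1 whether or not MRD was tested. Neither the category list nor the reasons for a not-evaluable response in SAP 4.2.1 provides for a CR whose MRD status is unknown.

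**Related rate.** SAP 4.2.2 defines the 24-week CR rate through a best overall response of CR, and SAP 5.2.9.1 gives it an exact confidence interval.

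**The concern.** A patient in CR who was never tested for MRD and a patient in CR who tested positive both appear in the CR row. Missing MRD data are therefore treated as a result other than negative. Because testing is scheduled for almost nobody in the analysed population, the CR_MRD- row may mainly show how often a site happened to test.

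A reader of the study report could take a low CR_MRD- percentage as evidence that remissions were shallow, when the data show only that few were examined. Cohort 8 mixes two schedules, so its split between CR and CR_MRD- does not arise in the same way as in the other dose cohorts.

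The split may also reach a rate with a planned interval. If the 24-week CR rate counts only patients whose best response is labelled CR, a confirmed negative MRD result removes a patient from that rate.

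**Working it through.** **1. The plan's own figures.** SAP 2.3.2 gives probabilities for 10 expansion patients.
- At a true CR rate of 20%: no CR, 0.8^10 = 10.7%; at least one, 89.3%; at least two, 1 − 0.8^10 − 10 × 0.2 × 0.8^9 = 62.4%. The plan states 11%, 89% and 62.4%.
- At least one AE: 1 − 0.9^10 = 65.1%, 1 − 0.95^10 = 40.1%, 1 − 0.99^10 = 9.56%. The plan states 65%, 40% and 9.6%.

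All reproduce. No figure is given for MRD.

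**2. Share of patients with a scheduled MRD test.** Let n1 be the Part 1 size (planned 24 to 30; the actual number is redacted) and n2 the Part 2 size. Then f = n2/(n1 + n2).
- As planned, n2 = 10: 10/34 = 29.4% to 10/40 = 25.0%.
- As enrolled, n2 = 1: 1/25 = 4.0% to 1/31 = 3.2%.

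So about 96-97% have no scheduled test.

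**3. Expected reported CR_MRD- rate.** Let t be the true rate and q the chance that a Part 1 MRD-negative CR is identified from local testing. The documents give neither, so both are assumptions. Then the expected reported rate is t × [f + (1 − f) × q]. With t = 10%:

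| q | n1 = 24, n2 = 1 | n1 = 30, n2 = 1 |
|---|---|---|
| 0 | 0.40% | 0.32% |
| 0.25 | 2.80% | 2.74% |
| 0.5 | 5.20% | 5.16% |
| 1 | 10.0% | 10.0% |

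For example, with n1 = 24 and q = 0.5: 0.10 × (0.04 + 0.96 × 0.5) = 0.052. At q = 0, t = 5% gives about 0.2% and t = 20% gives 0.6-0.8%.

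**4. Chance that the row reads zero at t = 10%.** If only the one Part 2 patient is tested: 1 − 0.10 = 90%. If all 25 to 31 are tested: 0.9^25 = 7.2% to 0.9^31 = 3.8%.

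**5. Which summaries depend on the split.**
- cCR-1, cCR-2, cCR-3, ORR and CBR (SAP 4.2.2) and EFS (SAP 4.2.5) each name CR_MRD- alongside CR. Moving a patient between the two rows changes none of them.
- The 24-week CR rate names only CR. Take two patients with the same remission, one tested and negative, one untested. On a literal reading the first leaves the numerator and the second stays. The same section goes on to use the date of first CR, so another reading is possible; the text does not settle it.
- Duration of CR (SAP 4.2.3) and time to CR (SAP 4.2.4) carry the same ambiguity.

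**The case against.** The strongest reply is that Part 1 patients are not shut out of the category. Their marrow at tumor evaluations has local immunophenotyping and molecular testing, Appendix 8 asks only for a negative RT-qPCR or flow result, and the investigator assigns the response. A Part 1 investigator with a suitable local result could record CR_MRD-. The eCRF sentence in Protocol 6.1.10.3 concerns the screening work-up; it does not show that later response categories go unrecorded, and the CRF itself is not available here.

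This stands, and it limits the point. A reader might infer that nearly every patient cannot be scored, or that the table must show 0/30 with an interval of 0 to 11.6%. The documents support neither. The first overlooks local testing. The second is the extreme q = 0, and SAP 5.2.9.1 plans no interval for individual response rows.

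The reply does not remove the problem. The amendment summary lists the MRD row as an addition to Table 2 only, with the rationale "Evaluation was added to allow for proof-of-concept evaluation of relevance of minimal residual disease", which suggests that the sponsor did not regard the routine local work-up as an MRD evaluation. Appendix 17 lists AML markers but no MRD threshold or sensitivity. Nothing in the SAP separates a tested CR from an untested one.

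It is also fair that the MRD-negative rate is not a named endpoint, that a single response row in cohorts of three or more patients says little by dose in any case, and that no hypothesis is tested. These points limit the consequences but do not justify reporting an unknown status as though it were known.

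**Conclusion.** The point holds in a bounded form. Scheduled MRD testing covers one of about 25 to 31 patients, and the SAP divides by all of them with no category for unknown status. The CR_MRD- percentage is therefore a lower bound, provided that each recorded negative is a true negative. The shortfall runs from almost complete to none, depending on how often local testing identified MRD-negative remissions; the documents do not give that share. The sizes rest on the planned Part 1 number and on an illustrative true rate of 10%.

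A reader might go further and infer that the response results as a whole are biased. They are not: the composite CR rates, ORR, CBR and EFS pool CR_MRD- with CR. Beyond the CR_MRD- and CR rows, only the bare 24-week CR rate and the duration of and time to CR are exposed, and only because their wording leaves open whether CR_MRD- is included.

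**What to change.** In SAP 5.2.9.1:
- Replace the CR_MRD- and CR lines by three: CR, MRD-negative; CR, MRD-positive; CR, MRD not assessed. A CR whose test status cannot be established goes in the third.
- Report MRD-negativity only among patients in CR with a post-baseline MRD result, and show the number tested.

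In SAP 4.2.2 to 4.2.4:
- Define the 24-week CR rate, duration of CR and time to CR to include CR_MRD-. In practice this means using the existing cCR-3 versions in their place.
- Keep the cCR-1 and cCR-2 rates with their confidence intervals. They are unaffected, and dropping them would lose planned information.

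The cost is SAP wording and one table layout, with no new data collection. The MRD line will rest on very few patients, which is the true position.

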8.6.7 Progression of Hematological Malignancy Under Study

Events that clearly conform to expected progression of underlying disease should not be recorded as AEs. These data are only used for efficacy evaluation. Determination of clinical progression is at the discretion of the investigator and may include both objective and subjective data. The continuation decision should be made by the investigator in consultation with the sponsor. In most cases, expected mode of progression will be evaluated based on efficacy evaluation criteria suitable for studied tumor type. In a small number of cases, clinical progression is determined based on aggregation of clinical features. However, progression should be demonstrated using objective criteria. If it is uncertain whether a certain event is caused by progression of disease, it

should be reported as an AE. If such event leads to death, then it should be reported with reference to description of “Death” (see Section 8.6.8).

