5	Early discontinuation (lost to follow-up or withdrawal of consent) of study without death or relapse (or PD)	Date of last adequate tumor assessment	Censored
6	Subsequent anti-tumor therapy started prior to relapse (or PD) or death	Date of last adequate assessment prior to or on date of initiation of subsequent anti-tumor therapy	Censored
7	Death or relapse (or PD) after two or more consecutive missed or inadequate tumor assessment visits	Date of last adequate tumor assessment prior to missed visits	Censored

PD is only applicable for the duration of objective response.

Note: An adequate tumor assessment is defined as an assessment where the Investigator determined response is CR_{MRD}-, CR, CRh, CRI, MLFS, PR, SD, and PD. If PD and subsequent anti-cancer therapy occur on the same day, will assume that the progression was documented first, e.g. outcome is progression and the date is the date of the assessment of progression.

(a) Determination of one missing or inadequate assessment

The following provides the rules for determining whether one tumor assessments is missed, of note, the relative day in the rules refers to the first dose date of study drug from Cycle 1 in continuous cycle.

- If the tumor assessment date is prior to day 1 of week 23 (relative day $< (24 - 1) \times 7 + 1 = 162$), and the difference between the tumor assessment date and the next adjacent adequate tumor assessment ≥ 63 days (8 weeks * 7 + 7), then the tumor assessment is considered as occurring after one missing tumor assessment;
- If the tumor assessment date is on or after day 1 of week 23 (relative day $< (24 - 1) \times 7 + 1 = 162$), and the difference between the tumor assessment date and the next adjacent adequate tumor assessment ≥ 98 days (12 weeks * 7 + 14), then the tumor assessment is considered as occurring after one missing tumor assessment.

(b) Determination of two or more consecutive missing or inadequate assessments

The following provides the rules for determining whether two or more consecutive tumor assessments are missed.

- If the tumor assessment date is prior to day 1 of week 15 (relative day $< (16 - 1) \times 7 + 1 = 106$), and the difference between the tumor assessment date and the next adjacent adequate tumor assessment ≥ 126 days ($= 2 * (8 \text{ weeks} * 7 + 7)$), then the tumor assessment is considered as occurring after two or more consecutive missing tumor assessments;

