4.2.7. Progression-free Survival

Progression-free Survival (PFS) is defined as the time (months) from the start of study treatment from Cycle 1 in continuous cycle (i.e. not from the date of single oral dose from the PK week for the dose escalation part) to disease progression, or relapse, or death due to any cause, whichever occurs first. More specifically, PFS will be determined using all the assessment data up until the last evaluable visit prior to or on the date of

- (i) disease progression (at least 2 cycles of study drug should be administered to determine PD) or relapse as defined by 2017 ELN criteria for AML patients, or
- (ii) withdrawal of consent; or lost to follow-up, or
- (iii) receiving subsequent anti-tumor therapy, whichever is earlier.

Patients without report of PD or death due to any cause at the time of analysis are censored as described in [Table 7](#) below.

Table 7 Outcome and Event or Censoring Dates for PFS

Rule	Situation	Date of Progression or Censoring	Outcome
------	-----------	----------------------------------	---------

1	PD/relapse documented between schedule tumor assessment visit or after one missing tumor assessment visit	Date of first documented disease progression/relapse	Event
2	Death without PD/relapse between schedule tumor assessment visit or death on or before the second scheduled visit or death after one missing tumor assessment visit	Date of death	Event
3	No baseline or post-baseline tumor assessments available and subject dose not die	Date of first administration of study treatment	Censored
4	No death or PD/relapse by the time of data cut-off for final analysis	Date of last adequate tumor assessment prior to or on analysis data cutoff date	Censored
5	Early discontinuation (lost to follow-up or withdrawal of consent) of study without death or PD/relapse	Date of last adequate tumor assessment	Censored
6	Subsequent anti-tumor therapy started prior to PD/relapse or death	Date of last adequate assessment prior to or on date of initiation of subsequent therapy visit	Censored
7	PD/relapse or death after missed or inadequate two or more consecutive tumor assessment visits	Date of last adequate tumor assessment prior to missed visits or date of first administration of study treatment (if no post-baseline tumor assessment)	Censored

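### Investigator-noted clinical progression with no post-dose tumor assessment is PD for best overall response but not a PFS event; unless an early death intervenes, PFS is censored, at first dose if the patient is alive

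*SAP*

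**What the plan says.** **Best overall response.** SAP 4.2.1 gives PD to "subjects who do not have post-dose tumor assessment, but have clinical progression as noted by the investigator or have died due to any cause" before the second post-dose assessment. That sentence carries no ELN condition and no two-cycle condition. The paragraph before it does: a patient whose only assessment shows PD after one cycle is not evaluable. SAP 3.1.5 also admits clinical progressors without a post-dose assessment to the response evaluable set, provided they have a baseline assessment. The plan therefore foresees this patient.

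**PFS.** SAP 4.2.7 uses "disease progression (at least 2 cycles of study drug should be administered to determine PD) or relapse as defined by 2017 ELN criteria". The Table 7 rows that matter here are:
- Rule 2 (event at date of death): among others, "death on or before the second scheduled visit or death after one missing tumor assessment visit".
- Rule 3 (censored at first administration): "No baseline or post-baseline tumor assessments available and subject dose not die". Table 8 ranks this reason first.
- Rule 6 (censored at the last adequate assessment): "Subsequent anti-tumor therapy started prior to PD/relapse or death".
- Rule 7 (PD, relapse or death after two or more missed visits): censored at the last adequate assessment, or at "date of first administration of study treatment (if no post-baseline tumor assessment").

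**Protocol.** Section 8.6.7 says "Determination of clinical progression is at the discretion of the investigator and may include both objective and subjective data", but also describes such cases as few and asks that progression be shown by objective criteria. Section 9.2.7 defines PFS by disease progression or death without restricting how progression is established.

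SAP section 7, which lists changes from the protocol, does not mention the difference between the two endpoints.

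**The concern.** One clinical fact is treated in two ways. In the response table the patient has failed. In PFS the same patient, if alive, contributes no follow-up and no failure. The reason for censoring is that the patient got worse before an assessment was made, so censoring is not independent of prognosis. Taking known early failures out of the risk set at time zero raises the Kaplan-Meier curve.

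Later data may not repair this. Under Protocol 6.1.14 and 6.1.19, tumor assessment after treatment continues only for patients who stopped for reasons other than progression. The first scheduled on-treatment assessment is at Cycle 3 Day 1 (Week 8). SAP 5.1.1 presents efficacy by dose level, and Protocol 4.1.1 sets a minimum of three patients per level, so one patient can move an estimate visibly. Three-month PFS is one of the example landmarks in SAP 5.2.9.2.

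**Working it through.** **Step 1: the plan's own gap.** The line between Rule 2 and Rule 7 depends on what counts as two missed visits. For the early period SAP 4.2.3 gives 2 × (8 × 7 + 7) = 126 days, which reproduces. Beyond that gap, "then the tumor assessment is considered as occurring after two or more consecutive missing tumor assessments". The rule is written for intervals between assessments. Counting from Day 1 for a patient with no post-baseline assessment is my reading; it puts the boundary at Day 127.

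**Step 2: trace the patient.** Best response is PD by clinical progression, with no post-dose assessment.

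| Later course | Rule | PFS |
|---|---|---|
| Alive | 3 | Censored at first dose |
| Alive, new therapy started | 3 and 6; Table 8 ranks 3 first | Censored at first dose |
| Dies Day 60, no new therapy | 2 | Event, Day 60 |
| Dies Day 126, no new therapy | 2 | Event, Day 126 |
| Dies Day 127 or later, no new therapy | 7 | Censored at first dose |
| New therapy Day 45, dies Day 60 | 6 | Censored, no usable date |

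In the last row, Rule 6 asks for the last adequate assessment. The note to Table 7 defines adequate by an investigator-determined response category, and this patient has no post-baseline assessment to supply one.

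By the SAP formula, censoring at first dose gives (0 + 1)/30.4375 = 0.03 months. An event on an assumed Day 42 would give 42/30.4375 = 1.38 months.

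**Step 3: illustrate the size.** All data here are assumed. Take 10 patients: k clinical progressors on Days 30, 40 or 50 with no post-dose assessment, three ELN progressions on Day 57, and the rest progression-free past Day 91. The clinical progressors either survive past Day 91 or start new therapy before dying, and Rule 6 is taken to censor at first dose. Three-month PFS is then (7 − k)/10 if clinical progression counts and (7 − k)/(10 − k) under Table 7.

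- k = 1: 6/10 = 60% against 6/9 = 67%
- k = 2: 5/10 = 50% against 5/8 = 62.5%
- k = 3: 4/10 = 40% against 4/7 = 57%

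A second assumed set has the other patients' events spread between Days 57 and 300, and clinical progression on Day 42 in patients who stay alive. Counting it gives 70% throughout; Table 7 gives 77.8%, 87.5% and 100% for k = 1, 2 and 3. The direction is the same and the size depends on the assumptions.

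At the minimum cohort size of three, with one such patient alive and the other two progression-free past Day 91, the figures are 2/3 = 67% against 2/2 = 100%.

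**The case against.** The case for leaving PFS alone has five parts.

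- **Objective progression is a legitimate choice.** Protocol 8.6.7 asks for objective criteria, and the footnotes to Appendix 8 warn that rising blasts under IDH inhibition may not mean progression. This stands against making clinical progression the main PFS event without argument. It does not explain why the same judgement is accepted for best response.
- **The case may be rare.** Protocol 6.1.10.3 and 6.1.14 schedule an assessment at end of treatment, and 6.1.18 places that visit within 7 days (± 3) of the last dose. A reader might infer from the Week 8 schedule that rapid progressors routinely leave unassessed. The documents do not support that; the end-of-treatment assessment must be missed or inadequate.
- **Early deaths are events.** Protocol 2.3.1 cites a median survival of about 1.5 months in refractory AML. If all three clinical progressors in the first illustration died before Day 91 without new therapy, Rule 2 would count them and both methods would give 40%. This stands and limits the size.
- **Counting clinical progression creates a new oddity.** A judgement on Day 30 would be an event, while ELN PD documented after one cycle would not. This stands, but SAP 4.2.1 already has that oddity for best response, so the two-cycle condition needs stating in both places.
- **Little else moves.** PD instead of not evaluable leaves ORR and CBR unchanged, OS counts deaths regardless of new therapy, and no hypothesis is tested. This stands and sets the severity.

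**Conclusion.** The mismatch is real and unexplained. Clinical progression with no post-dose tumor assessment is PD for best overall response and is not a PFS event. PFS is censored at first dose if the patient is alive or dies after two or more missed visits. It is censored without a usable date if new therapy precedes death. A death on or before the second scheduled visit, or after one missed visit, is an event when no new therapy has intervened. Where censoring applies, it biases descriptive PFS upward.

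Two stronger readings are tempting and do not hold. One is that every clinical progressor is censored at Day 1; Rule 2 excludes that. The other is that lack of a marrow is enough. The SAP condition is no post-dose tumor assessment, and under Appendix 8 progression can rest on peripheral blasts or new extramedullary disease.

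The 40% against 57% contrast is an illustration, not an estimate of bias in this trial. The number affected cannot be known from the documents. No 10-patient expansion cohort exists either: the note to SAP Table 13 says one patient was enrolled in Part 2 and is combined with Cohort 8.

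Severity is minor, because PFS is a secondary descriptive endpoint with no hypothesis test.

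**What to change.** Reconcile SAP 4.2.7 and Table 7 with 4.2.1 before database lock:

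1. Report PFS both ways. One analysis uses ELN PD, relapse or death only. The other also counts investigator-noted clinical progression without a post-dose assessment as an event on its recorded date, if that precedes any new therapy.
2. State which analysis is the main one and why, and record the choice in SAP section 7.
3. State how the two-cycle condition applies to clinical progression, in the same terms for best overall response and for PFS.
4. Give Rule 6 a censoring date for patients with no post-baseline assessment.

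The cost is SAP wording and one extra derivation. The second analysis relies on investigator judgement and on a recorded date of clinical progression. The CRF is not among the documents, and Protocol 6.2.1.1 mentions only the primary reason for discontinuation, so the availability of that date needs checking. One of the two PFS results will look slightly less favourable.
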